7.5.1.4 Relationship of AE

The number of TEAEs and the number and percentage of subjects with TEAEs, as classified by SOC and PT will also be summarized by relationship to study drug (Mirabegron/Placebo, Tamsulosin). In the subject count, if a subject has multiple TEAEs

with the same SOC or PT, but with differing relationship, then the subject will be counted only once with the highest degree of relationship. In the adverse event count, the adverse events will be presented in each category they were classified to.

7.5.1.5 Onset/Prevalence/First Onset of AE (Time Intervals)

The number and percentage of subjects with TEAEs, as classified by SOC and PT will be summarized in the following categories for each treatment group by time interval.

- Onset of AE: For each adverse event in a particular interval, a subject will be counted if there is an onset of a treatment-emergent adverse event regardless of onset in other intervals.
- Prevalence of AE: For each adverse event in a particular interval, a subject will be counted if the adverse event started, continued, or stopped during that interval.
- First Onset of AE: For each adverse event only the earliest onset will be counted if there is more than one onset of that adverse event.

Time intervals will be categorized according to the following categories:

- less than 14 days;
- at least 14 days, less than 28 days;
- at least 28 days, less than 56 days;
- at least 56 days, less than 84 days; and
- 84 days or more.

7.5.1.6 Subgroup Analysis of AE

The number and percentage of subjects with TEAEs, as classified by SOC and PT will be summarized for each treatment group by subgroups defined in section [7.8](#).

7.5.1.7 AEs Reported During Screening Period by SOC and/or PT

The number and percentage of subjects with AEs reported during screening period, as classified by SOC and PT will be summarized for each treatment group. Summaries will be provided for:

- AEs,
- serious AEs.

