7.5 Analysis of Safety

The safety analysis will be performed on the SAF.

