7.5.1 Adverse Events

Adverse events will be recorded at each visit. The incidence and severity (mild, moderate, or severe) of TEAEs will be tabulated.

Adverse events will be coded using the MedDRA dictionary.

Adverse events reported during the double-blind Treatment period will be analyzed as follows:

- The number and percentage of subjects with AEs, SAEs, AEs leading to discontinuation, and AEs related to study drug will be summarized by System Organ Class (SOC), Preferred Term (PT), and treatment group. The treatment groups will be compared using Fisher's Exact test, with a two-sided 95% confidence interval and 5% significance level. The number and percentage of AEs, by severity, will also be summarized. All AEs will be displayed in a listing, by subject.

Adverse events reported during the Screening period will be analyzed as follows:

- The number and percentage of subjects with AEs and the number and percentage of subjects with SAEs will be summarized by SOC and PT. A two-sided 95% confidence interval will be presented. The number and percentage of subjects with AEs by severity will also be summarized.

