5.3 Safety Analysis Set (SAF)

The SAF consists of all subjects who received at least 1 dose of double-blind study medication.

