7 STATISTICAL METHODOLOGY

7.1 General Considerations

Assessment at Visit 2 (Day 1) will be treated as baseline for efficacy and safety analysis.

The End of Treatment assessment is defined as the last post-Baseline assessment during the double-blind study period for which the primary efficacy data are available.

For continuous variables, descriptive statistics will include the number of subjects (n), mean, standard deviation, minimum, Q1 (25th percentile), median, Q3 (75th percentile) and maximum. Frequencies and percentages will be displayed for categorical data. Percentages by categories will be based on the number of subjects with no missing data, i.e. will add up to 100%.

Summaries based on FAS and PPS (e.g. disposition, baseline and efficacy data) will be presented by planned treatment group, unless specifically stated otherwise. Safety analysis and other summaries based on SAF will be presented by actual treatment received.

All statistical comparisons will be made using two sided tests at the $\alpha=0.05$ significance level unless specifically stated otherwise. All null hypotheses will be of no treatment difference, all alternative hypotheses will be two-sided, unless specifically stated otherwise.

All data processing, summarization, and analyses will be performed using Windows SAS[®] Version 9.4. Specifications for table, figures, and data listing formats can be found in the Tables, Listings and Figures (TLF) specifications for this study.

For the definition of subgroups of interest please refer to section [7.8](#)

Total and subscale score of OABSS, IPSS and OAB-q are as follows:

Name of score	Subscale score	Calculation	Range
IPSS (Question 1-7 and Quality Life Item)	Storage Subscale	Sum of Question 2,4 and 7	0-15
	Voiding Subscale-1	Sum of Question 3, 5 and 6	0-15
	Voiding Subscale-2	Sum of Question 1, 3, 5 and 6	0-20
	Quality of Life Item	-	0-6
	Total Index Score	Sum of Question 1 to 7	0-35
OABSS (Question 1-4)	Daytime frequency	Question 1	0-2
	Nighttime frequency	Question 2	0-3
	Urgency	Question 3	0-5
	Urgency incontinence	Question 4	0-5
	Total Score	Sum of Question 1 to 4	0-15
OAB-q (Question 1-33)	Symptom bother	Sum of Q1-8	0-100
	Coping	Sum of Q9,11,16,21,22,26,32,33	0-100
	Concern	Sum of Q12,13,14,19,23,25,29	0-100
	Sleep	Sum of Q10,15,17,24,30	0-100
	Social Interaction	Sum of Q18,20,27,28,31	0-100
	Total Health-Related Quality of Life scores	Sum of OAB-q subscale scores (Coping, Concern, Sleep, Social Interaction)t	0-100

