7.5 Analysis of Safety

All analysis of safety will be presented by treatment group for SAF, unless specified otherwise.

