7.5.1.8 Severity of AEs Reported During Screening Period

The number of TEAEs and the number and percentage of subjects with AEs reported during screening period, as classified by SOC and PT will also be summarized by severity. The method used for this analysis will be identical to the analysis described in section

[7.5.1.3](#)

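### The run-in AE tables cover only subjects who went on to a double-blind dose, so events that ended participation during run-in are not summarised by term, seriousness or severity

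*SAP*

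**What the plan says.** Before randomisation every subject takes tamsulosin 0.2 mg plus mirabegron placebo for 4 weeks (protocol 5.1.1).

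For adverse events in that period, SAP 7.5.1.7 plans counts and percentages of subjects with AEs and with serious AEs "reported during screening period, as classified by SOC and PT will be summarized for each treatment group". SAP 7.5.1.8 adds a severity table: "The method used for this analysis will be identical to the analysis described in section" 7.5.1.3. Neither section names an analysis set, so the general rule of SAP 7.5 applies: "All analysis of safety will be presented by treatment group for SAF, unless specified otherwise". SAP 5.3 defines that set: "The SAF consists of all subjects who received at least 1 dose of double-blind study medication". SAP 7.1 fixes the column labels: "Safety analysis and other summaries based on SAF will be presented by actual treatment received".

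In the protocol, section 7.5 states: "The safety analysis will be performed on the SAF". Section 7.5.1 then has a separate block beginning "Adverse events reported during the Screening period will be analyzed as follows", under which "The number and percentage of subjects with AEs and the number and percentage of subjects with SAEs will be summarized by SOC and PT". That block also specifies a two-sided 95% confidence interval and does not mention treatment group.

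SAP 7.2.1 separately counts discontinuations in the screening period by primary reason, for all subjects combined.

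**The concern.** The run-in is a dosed period with study-supplied drug, and its AE tables should describe those who were dosed in it. Here, entry to the table depends on something that happens afterwards: a double-blind dose. A man who leaves because of an adverse event in run-in is removed from the table by the event that the table is meant to report.

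The loss can be informative in other ways. Exclusion criterion 32 (protocol 3.3) reapplies the Visit 1 exclusions at Visit 2, and these include a residual volume above 100 mL and postural hypotension or syncope. Protocol 6.1 lists an AE or SAE as a reason for discontinuation. SAP 7.5.1.9 names cardiovascular events, blood pressure and urinary retention as AEs of special interest.

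At stake is the completeness of the run-in safety report: which events ended participation, how severe they were and whether they were serious.

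**Working it through.** **Step 1. Trace who is in the table.**

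| Question | Source | Answer |
|---|---|---|
| How are screening AEs grouped? | SAP 7.5.1.7 | By treatment group; no set named |
| Which set applies by default? | SAP 7.5 | SAF |
| Do 7.5.1.7 or 7.5.1.8 override it? | SAP 7.5.1.7, 7.5.1.8 | No |
| Who is in the SAF? | SAP 5.3 | Subjects with a double-blind dose |
| Which arm label is used? | SAP 7.1 | Treatment actually received |
| Does the protocol use another set? | Protocol 7.5 | No, also the SAF |

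A subject who stops in run-in has no double-blind dose and no arm, so he is outside these tables. So is a subject who is randomised but never dosed in the double-blind period. Neither document defines a set of all subjects dosed in run-in.

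**Step 2. Look for another summary that covers them.** Disposition (SAP 7.2.1) gives a count by primary reason. It can show how many left because of an AE, but not the event term, its severity or its seriousness.

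**Step 3. Compare the two documents.** They agree on the SAF. They differ in two respects: the SAP adds the arm split, and it plans no confidence interval for this table where protocol 7.5.1 specifies one. In addition, SAP 7.5.1.8 counts TEAEs in a screening-period table, although under protocol 5.5.1.1 a screening event that resolves or does not worsen is not a TEAE.

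**Step 4. Size.** The plan states no figure for this table. The only design figure needed is the 550 to be randomised (SAP 4). Its basis reproduces: 2 × (1.960 + 1.282)² × 2.4² / 0.7² = 247.1, rounded up to 248 per group; 248 / 0.9 = 275.6, against the stated 275. The present point does not touch this calculation.

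The documents give no run-in loss rate. Let d be the share of run-in-dosed subjects who do not reach a double-blind dose (assumption), and take all 550 randomised as dosed. The number left out is 550 / (1 − d) − 550:

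| d (assumed) | Dosed in run-in | Left out |
|---|---|---|
| 10% | 611 | 61 |
| 20% | 688 | 138 |
| 30% | 786 | 236 |
| 40% | 917 | 367 |

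These are people, not events. If a share a of all run-in-dosed subjects leaves because of an AE, with a = 1% to 3% and d = 20% (both assumed), then 0.01 × 687.5 = 6.9 to 0.03 × 687.5 = 20.6, or about 7 to 21 such subjects, would not be tabulated.

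**Step 5. Direction of any bias in the overall rate.** Let p be the AE rate among those who continue, and suppose that those who leave for other reasons report no AE. The rate in all dosed subjects is p(1 − d) + a; the planned table shows p. With p = 5% (assumed):

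- d = 20%, a = 3%: 0.05 × 0.80 + 0.03 = 7.0%, so the table is too low.
- d = 20%, a = 1%: 0.05 × 0.80 + 0.01 = 5.0%, so there is no difference.
- d = 30%, a = 1%: 0.05 × 0.70 + 0.01 = 4.5%, so the table is too high.

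The sign depends on quantities that the documents do not give.

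**The case against.** The best case against the point has five parts.

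- **The SAF restriction is inferred from a default.** This is true: SAP 7.5.1.7 names no set, and SAP 7.1 leaves table formats to separate TLF specifications, which may hold an overall column. But the default is written as binding unless overridden, and nothing in the SAP overrides it.
- **The SAP follows the protocol on population.** This stands. A reader might infer from protocol 7.5.1 that the SAP narrowed the population, but protocol 7.5 has the same SAF rule. Both documents need attention.
- **Run-in leavers are not lost altogether.** A reader might infer that they appear in no summary. Disposition counts them by primary reason, and SAEs remain subject to 24-hour reporting (protocol 5.5.5). What is missing is the tabulation by term, seriousness and severity.
- **The arm split has a use.** A reader might call a split by an arm not yet assigned meaningless. It is not: a screening event becomes a TEAE only if it worsens, so pre-treatment events by arm help in reading the TEAE tables. The defect is the lack of an overall column on the right set.
- **A downward bias is not shown.** A reader might infer that run-in AE rates are too low. Subjects also leave for diary thresholds, compliance or urine volume (protocol 3.2 and 3.3), and Step 5 shows that the overall rate can err either way.

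The study question is mirabegron against placebo, run-in contains no mirabegron, and subjects must already have taken tamsulosin for at least 4 weeks. This limits the importance of the point, and it stands.

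**Conclusion.** The point holds as a minor one about completeness. As written, the screening-period AE, SAE and severity tables leave out every subject without a double-blind dose. Events that led to run-in exit are therefore necessarily under-counted: such subjects contribute zero to these tables whatever happened.

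This rests on reading the SAP 7.5 default literally, and the unseen table specifications could soften it. The number left out, about 61 to 367, rests wholly on an assumed loss of 10% to 40%. The documents support neither a particular loss rate nor a direction of bias in the overall run-in AE rate. The efficacy analyses and the double-blind safety comparison are not affected.

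Two smaller defects are clear from the text: the confidence interval in protocol 7.5.1 is absent from SAP 7.5.1.7, and SAP 7.5.1.8 counts TEAEs where it should count AEs.

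**What to change.** - In SAP section 5, define a run-in safety set: all subjects with at least one dose of screening-period drug. Reconcile this with protocol 7.5, which now places all safety analysis on the SAF.
- In SAP 7.5.1.7 and 7.5.1.8, tabulate screening AEs, SAEs and severity on that set in one overall column, with the two-sided 95% confidence interval from protocol 7.5.1.
- Show either randomised versus not randomised, or AEs leading to run-in discontinuation, so that the events that ended participation are visible.
- Keep the split by later arm in the SAF, if wanted, as a supplementary comparability display.
- In SAP 7.5.1.8, replace the count of TEAEs by a count of AEs.

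The cost is one population flag and one table column. The data should already exist: protocol 8.1.1 limits data entry to minimal screening-log items only for subjects who leave before run-in drug is dispensed.

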7.5.1.8 Severity of AEs Reported During Screening Period

The number of TEAEs and the number and percentage of subjects with AEs reported during screening period, as classified by SOC and PT will also be summarized by severity. The method used for this analysis will be identical to the analysis described in section

[7.5.1.3](#)

7.5.1.9 AEs of Special Interest

Following AEs of special interest are defined:

- Cardiovascular events
- Blood pressure
- Urinary retention

The number of TEAEs of special interest and the number and percentage of subjects with TEAEs of special interest, as classified by SOC and PT will be summarized for each treatment group.

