1.4.1.2 Korean Labeling

The following information on adverse reactions is from the Korean labeling for Betmiga (mirabegron) prolonged-release 25 mg and 50 mg tablets (April 2015):

Adverse reactions

(1) Adverse reactions reported in foreign clinical trials

The safety of mirabegron was evaluated in 8433 subjects with OAB, of which 5648 received at least 1 dose of mirabegron in the Phase 2/3 program, and 622 subjects received mirabegron for at least 1 year. In the three 12-week Phase 3 double-blind, placebo-controlled studies, 88% of the subjects completed treatment with mirabegron and 4% discontinued from the study due to AEs. Most adverse drug reactions were mild-to-moderate in severity.

The most common adverse reactions reported in subjects treated with mirabegron 50 mg were urinary tract infections (UTI; 2.9%) and tachycardia (1.2%). Tachycardia led to discontinuation in 0.1% of subjects receiving mirabegron 50 mg. No cases of UTI in patients receiving mirabegron 50 mg led to discontinuation from the study. Serious adverse reactions included atrial fibrillation (0.2%).

The adverse reactions observed during the long-term (1-year) active-controlled (muscarinic antagonist) study were similar in nature and severity to those observed in the three 12-week placebo-controlled studies.

Adverse Reactions Observed in Subjects Treated with Mirabegron in Three Phase 3, Double-Blind, Placebo-Controlled Studies

MedDRA System Organ Class	Common ARs (1/100≤ , <1/10)	Uncommon ARs (1/1,000≤ , <1/100)	Rare ARs (1/10,000≤ , <1/1,000)
Infections and infestations	Urinary tract infection	Vaginal infection	
Eye disorders			Eyelid oedema
Cardiac disorders	Tachycardia	Palpitation Atrial fibrillation Blood pressure increased	
Gastrointestinal disorders		Dyspepsia Gastritis	Lip oedema
Skin and subcutaneous tissue disorders		Urticaria Rash Macular rash Papular rash Pruritus	Leukocytoclastic vasculitis Purpura
Musculoskeletal and connective tissue disorders		Joint swelling	
Urinary and reproductive system disorders		Vulvovaginal pruritus Cystitis	
Metabolism and nutrition system disorders		GGT increased AST increased ALT increased	

ALT = alanine aminotransferase; AR = adverse reaction; AST = aspartate aminotransferase; GGT = gamma-glutamyl transferase; MedDRA = Medical Dictionary for Regulatory Activities

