1.4.1.3 Clinically significant adverse drug reactions with mirabegron treatment

Identified risks with mirabegron treatment include increased heart rate and tachycardia as well as hypersensitivity reactions. Potential risks include QT prolongation, increased

blood pressure, UTI, urinary retention, fetal disorders after exposure during pregnancy, and events induced by increased exposure to CYP2D6 substrates. The risks of QT prolongation, increased heart rate, or increased blood pressure are greater with increasing exposure at supratherapeutic doses, and can be mitigated with optimal dose selection. The maximum therapeutic dose of mirabegron, based on the overall benefit-risk is 50 mg once daily. In patients with severe renal impairment or moderate hepatic impairment, the dose of mirabegron is 25 mg once daily. Further dose adjustments for renal impairment, hepatic impairment and concomitant use of strong CYP3A4 inhibitors may be required.

Overall, mirabegron at the therapeutic oral doses of 25 mg and 50 mg once daily is considered to be a safe and effective for the treatment of adult patients with OAB. The benefits of treatment exceed the risk associated with the use of the product. Mirabegron was approved in Japan in 2011, and to date has been approved in more than 50 countries, including the United States and European Union.

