7.5.1.2 Adverse events by SOC and/or PT

The coding dictionary for this study will be MedDRA (ver.18.1), which will be used to summarize AEs by SOC and PT.

The number and percentage of subjects with TEAEs, as classified by SOC and PT will be summarized for each treatment group. Summaries will be provided for:

- TEAEs,
- drug related TEAEs (Mirabegron/Placebo, Tamsulosin, Both),
- serious TEAEs,
- drug related serious TEAEs (Mirabegron/Placebo, Tamsulosin, Both),
- TEAEs leading to permanent discontinuation of study drug (Mirabegron/Placebo, Tamsulosin, Both),
- drug related TEAEs leading to permanent discontinuation of study drug (Mirabegron/Placebo, Tamsulosin, Both),
- TEAEs excluding serious adverse events that equal to or exceed a threshold of 2.0% in any treatment group, and
- Common TEAEs that equal to or exceed a threshold of 2.0% in any treatment group.

The treatment groups will be compared using Fisher's Exact test, with a two-sided 95% exact unconditional CI and 5% significance level.

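### Hypersensitivity, an identified mirabegron risk, is not an adverse event of special interest in the SAP, and no planned table combines it into one per-subject count by arm (minor)

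*SAP*

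**What the plan says.** Protocol 1.4.1.3 sorts the risks of mirabegron into two groups. On the first it says: "Identified risks with mirabegron treatment include increased heart rate and tachycardia as well as hypersensitivity reactions". The second group, potential risks, contains QT prolongation, increased "blood pressure, UTI, urinary retention, fetal disorders after exposure during pregnancy" and events from raised exposure to CYP2D6 substrates.

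SAP 7.5.1.9 ("Following AEs of special interest are defined") has three entries: cardiovascular events, blood pressure and urinary retention. Events in these categories, "as classified by SOC and PT will be summarized for each treatment group", are given as numbers and percentages. The section gives no list of terms for any category, no row for subjects with any event in a category, and no arm difference, interval or test.

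The general tables in SAP 7.5.1.2 are fuller: "The number and percentage of subjects with TEAEs, as classified by SOC and PT will be summarized for each treatment group". For these, "The treatment groups will be compared using Fisher's Exact test, with a two-sided 95% exact unconditional CI and 5% significance level". One of the eight summaries listed there is "Common TEAEs that equal to or exceed a threshold of 2.0% in any treatment group".

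The Korean labelling table in Protocol 1.4.1.2 lists, under skin disorders, "Urticaria Rash Macular rash Papular rash Pruritus" as uncommon and leukocytoclastic vasculitis and purpura as rare. It lists eyelid oedema under Eye disorders and lip oedema under Gastrointestinal disorders, both rare. The Japanese labelling table in Protocol 1.4.1.1 has rash, urticaria and pruritus, all under Skin.

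**The concern.** The special-interest list does not follow the protocol's own ranking of risks. Two potential risks are singled out and one identified risk is left out, with no reason given. The other identified risk, tachycardia and increased heart rate, fits under cardiovascular events, so hypersensitivity is the only identified risk without a grouping.

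Safety and tolerability against placebo is the secondary objective (SAP 3.1.2). A hypersensitivity reaction can be coded to any of several terms in more than one organ class, and most of those terms are expected to be infrequent. A reader of the study report who wants to know how many men in each arm had any such event could not read the number from a planned table. Adding up term rows would count a man with two terms twice, and the Skin row answers a broader question.

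**Working it through.** **1. Risk list against special-interest list**

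| Risk | Status in Protocol 1.4.1.3 | In SAP 7.5.1.9? |
|---|---|---|
| Increased heart rate, tachycardia | Identified | Fits under cardiovascular events |
| Hypersensitivity reactions | Identified | No |
| Increased blood pressure | Potential | Yes |
| Urinary retention | Potential | Yes |

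**2. What the general tables already give.** SAP 7.5.1.2 counts each subject once per preferred term and once per organ class, by arm, with a test and an interval. Of nine candidate terms in the Korean label (urticaria, rash, macular rash, papular rash, pruritus, purpura, leukocytoclastic vasculitis, eyelid oedema, lip oedema), seven fall in the Skin row. The 2.0% threshold applies to only two of the eight summaries, so rarer terms still appear elsewhere.

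**3. Expected size at label frequencies.** Inputs: 275 men per arm (SAP section 4); the uncommon band of 1/1,000 to under 1/100 and the rare band of under 1/1,000 (Protocol 1.4.1.2). Assumption: these frequencies carry over to this trial.

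- One rare term: fewer than 275 × 0.001 = 0.275 men per arm. Eyelid and lip oedema together: fewer than 2 × 0.275 = 0.55.
- One uncommon term: 275 × 0.001 = 0.275 up to 275 × 0.01 = 2.75 men.
- Any of the five uncommon skin terms, if independent: 275 × (1 − (1 − p)^5), which is 1.37 at p = 0.001 and 13.48 at p = 0.01.

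Most of the expected events therefore lie inside the Skin row. The terms in the other two organ classes add little on average.

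**4. Illustration with assumed counts** (two-sided Fisher's exact test, 275 per arm; none of these counts comes from the documents)

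| Row | Mirabegron vs placebo | p |
|---|---|---|
| Pooled hypersensitivity | 9 vs 1 | 0.020 |
| Pooled hypersensitivity | 8 vs 1 | 0.038 |
| Pooled hypersensitivity | 7 vs 1 | 0.068 |
| Pooled hypersensitivity | 9 vs 2 | 0.063 |
| Pooled hypersensitivity | 8 vs 2 | 0.106 |
| Single term | 3 vs 0 | 0.25 |
| Single term | 2 vs 0 | 0.50 |
| Skin row, all of 8 vs 1 coded to Skin, no other skin events | 8 vs 1 | 0.038 |
| Skin row, two of the eight men with only lip or eyelid oedema | 6 vs 1 | 0.12 |
| Skin row, all of 8 vs 1 plus 5 men per arm with only non-allergic skin events | 13 vs 6 | 0.16 |

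The Skin row equals the pooled row if every event is coded to Skin and nothing else is. It weakens mainly through dilution by other skin events. Coding outside Skin matters less, since at label frequencies two men with only lip or eyelid oedema would be unusual. The pooled result is also fragile: one man fewer on mirabegron or one more on placebo takes 8 vs 1 past 0.05. The table shows how pooling can matter and does not predict a result.

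**The case against.** The strongest case against is that little is missing. Every hypersensitivity-type term is counted per subject by arm and tested, and the Skin row already brings most of them together. A reader might infer from the omission that such events are never counted by arm, that they appear only as isolated terms, or that the 2.0% threshold hides them. SAP 7.5.1.2 contradicts all three.

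The choice of special-interest categories is also partly a matter of judgement. Nothing in the documents says that they must match the identified risks. The three chosen suit this combination: cardiovascular interaction with tamsulosin (Protocol 1.4.3) and urinary retention in men with BPH. Men with known hypersensitivity to mirabegron are excluded (exclusion criterion 24). The spread over three organ classes rests on the Korean label alone. The mirabegron label tables have no hypersensitivity heading, and the documents do not say which preferred terms make up this risk; counting purpura and vasculitis is a judgement. Term lists and any-event rows may stand in the table specifications that SAP 7.1 refers to, which are not among the documents.

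All of this stands and limits the point to a minor one. It does not supply a count of men with any hypersensitivity event, a reason for leaving out an identified risk, or an arm difference for the three categories that are listed.

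**Conclusion.** The point holds as an inexpensive improvement to safety reporting, not as an error that endangers a conclusion. An identified risk has no grouping while two potential risks do. Its terms are counted singly and by organ class, but never as one per-subject count by arm across organ classes. Separately, SAP 7.5.1.9 states no between-arm estimate for any special-interest category.

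Severity is minor. No data are lost, and the primary analysis is unaffected. The practical loss is a clean count: the Skin row is a fair proxy if few non-allergic skin events occur, and a poor one otherwise. This rests on the assumption that label frequencies roughly apply here, and on reading the listed label terms as hypersensitivity-type, which the documents imply but do not state. A reader might take the 8 vs 1 illustration as evidence that a real excess would be missed. The documents do not support that, since the counts are assumed, neighbouring counts do not reach 0.05, and the Skin row may show the same excess.

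**What to change.** In SAP 7.5.1.9, add hypersensitivity reactions as a fourth category. Define it by a list of MedDRA 18.1 preferred terms fixed before unblinding and built around the mirabegron label terms in Protocol 1.4.1.1 and 1.4.1.2. Terms found only in the tamsulosin label need not be included, because both arms take tamsulosin and such terms could dilute a mirabegron difference.

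Naming the category is not enough, because the section tabulates by organ class and preferred term. So for every special-interest category, add a row for subjects with at least one event, with the arm difference and the exact unconditional 95% CI already used in SAP 7.5.1.1. Term lists for the three existing categories should be fixed at the same time. If the sponsor prefers not to add the category, one sentence giving the reason would do.

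The cost is SAP wording, a term list before unblinding and one more table block. No new data are needed, and sample size and alpha do not change. The downside is one more descriptive comparison among many, which should be read as such.

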1.4.3 Potential Risks with Combined Treatment

Alpha-adrenergic receptor antagonists, like tamsulosin, are associated with cardiovascular side effects, such as orthostatic hypotension, syncope, tachycardia, and palpitations. An open-label, randomized, two-arm, two-sequence, crossover Phase 1 study in 48 healthy men aged 44 to 72 years of age evaluated the potential pharmacokinetic (PK) and cardiovascular interactions with concomitant tamsulosin and mirabegron treatment²⁴.

The effect of steady-state mirabegron 100mg/day on single-dose 0.4mg/day tamsulosin was evaluated in 1 treatment arm, and the effect of steady-state tamsulosin on single-dose mirabegron was evaluated in the second treatment arm. The PK results showed that with combined treatment, the maximum observed plasma concentration (C_{max}) and area under the drug concentration-time curve (AUC) for tamsulosin increased ~60%, and mirabegron exposure decreased by ~16%.

With respect to cardiovascular safety, the combined treatment resulted in no statistically significant changes in pulse rate (PR) or systolic blood pressure (SBP), compared to monotherapy, up to 12 hours after dosing. Although mean diastolic blood pressure (DBP) was significantly lower with combination treatment, the effect was small and not associated with orthostatic symptoms or an increase in positive orthostatic stress tests. Furthermore, orthostatic events were balanced across the treatment groups.

Thus, the results of this study showed that with co-administration, the increase in tamsulosin exposure and decrease in mirabegron exposure were not associated with clinically relevant pharmacodynamic interactions between the two drugs.

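### The adverse events of special interest have no term lists, no stated direction for blood pressure, and no planned between-arm estimate for any group

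*SAP*

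**What the plan says.** SAP 7.5.1.9 opens with "Following AEs of special interest are defined" and lists cardiovascular events, blood pressure and urinary retention. No preferred terms or standard query are attached to any of them, and blood pressure has no direction. The planned output is the number of events and that "the number and percentage of subjects with TEAEs of special interest, as classified by SOC and PT will be summarized for each treatment group". The section mentions no test, difference or interval.

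SAP 7.5.1.2 covers all TEAEs: "The number and percentage of subjects with TEAEs, as classified by SOC and PT will be summarized for each treatment group. Summaries will be provided" across several classes of event, and the arms are compared by Fisher's exact test "with a two-sided 95% exact unconditional CI and 5% significance level". SAP 7.5.1.1 plans the same for the overview table, with the difference taken as mirabegron minus placebo. Protocol 7.5.1 states that events "will be summarized by System Organ Class (SOC), Preferred Term (PT), and treatment group", also with Fisher's test, and does not mention special-interest groups.

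Sitting blood pressure and pulse rate are summarised as signed change from baseline by arm, at the site (SAP 7.5.3.1) and at home (SAP 7.5.3.2). Both summaries are descriptive.

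**The concern.** The events singled out in advance as important get less between-arm analysis than routine TEAEs. Safety and tolerability of adding mirabegron to tamsulosin is the secondary objective, and these groups are where its main risks would be read.

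Two gaps follow. First, no planned number answers how many more men had an event in a given group on mirabegron than on placebo. A modest excess spread over several terms may then be seen only as separate, imprecise rows. Second, the protocol discusses blood pressure in both directions. Section 1.4.1.3 lists increased blood pressure as a potential risk of mirabegron. Section 1.4.3 names orthostatic hypotension and syncope for alpha-blockers and, in the interaction study, reports "Although mean diastolic blood pressure (DBP) was significantly lower with combination treatment". A group total under an undirected heading would not show whether rises or falls drive it. If the terms are chosen after unblinding, the choice is open to challenge as data-driven.

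**Working it through.** **The plan's own figure.** The documents give no figure for the special-interest analysis. The only plan figure needed is the arm size (SAP 4). For the primary endpoint, n = 2(1.960 + 1.282)² × 2.4² / 0.7² = 247.0, rounded up to 248 per arm, as stated. Then 248/0.9 = 275.6 against 275 stated (275 × 0.9 = 247.5), which agrees closely. The safety set needs only one double-blind dose, so about 275 per arm is its upper limit and is used below.

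**Does SAP 7.5.1.2 already give the group estimate?** It compares arms by PT and by SOC. The Japanese labelling table in Protocol 1.4.1.1 places Blood pressure increased under cardiac disorders and Hypertension under vascular disorders. It also lists palpitations, tachycardia, extrasystoles and heart rate increased as separate terms. On that grouping no PT row and no SOC row equals either blood pressure or cardiovascular events. MedDRA 18.1 coding may place terms differently; without a term list this cannot be settled.

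**Illustration of a spread signal** (assumed counts, 275 per arm, different men in each term).
- One term at 3 vs 1: the two-sided Fisher p is 1 − P(2,2), where P(2,2) = C(275,2)² / C(550,4) = 37,675² / 3,771,305,175 = 0.376, so p = 0.62. The difference is 2/275 = 0.7 points.
- Five such terms: 15 vs 5. The difference is 10/275 = 3.6 points; Fisher p = 0.038.
- Newcombe 95% CI for 15 vs 5: the Wilson limits are 3.33% to 8.80% and 0.78% to 4.18%. Lower limit: 3.64 − √(2.12² + 2.37²) = 0.5. Upper limit: 3.64 + √(3.35² + 1.04²) = 7.1. The exact unconditional score-based interval, the type the SAP uses, is 0.4 to 7.2.
- If three of the five terms fall in one SOC and two in another, with no other events in either, the SOC rows are 9 vs 3 (p = 0.14) and 6 vs 2 (p = 0.29).

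**Power by assumed rate**, four terms, Fisher at two-sided 5%. Power is the sum over i, j of Bin(i; 275, p₁) × Bin(j; 275, p₀) over outcomes with p ≤ 0.05. The column for any term is 1 − (1 − per-term power)⁴, with terms taken as independent.

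| Rate per term | Per term | Any of four | Group total |
|---|---|---|---|
| 1.0% vs 0.25% | 3% | 12% | 53% |
| 1.5% vs 0.5% | 8% | 29% | 61% |
| 2.0% vs 0.5% | 20% | 59% | 89% |

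**Direction.** Assume rises of 12 vs 3 and falls of 10 vs 4. The undirected total is 22 vs 7, a difference of 15/275 = 5.5 points (p = 0.007). Rises alone at 22 vs 7 with no falls give the same total. The two cases mean different things clinically, and the total cannot tell them apart.

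**The case against.** The strongest reply is that most of the information is already planned. Every component PT and SOC is compared with a test and CI under SAP 7.5.1.2. If all the terms of a group fall in one SOC that holds no other events, that SOC row is the group estimate. If urinary retention is a single term, its PT row is enough. Signed blood-pressure changes are summarised at every visit, with plots of means and 95% CIs and shift scatter plots, so direction is visible in measured data. SAP 7.1 also leaves table layout to separate TLF specifications, which may define more than SAP 7.5.1.9 does. All of this stands, and it limits the point to the grouped difference and the missing definitions.

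A reader might infer that rises and falls will cancel in the blood-pressure group. The arithmetic allows it: rises of 12 vs 3 and falls of 3 vs 12 pool to 15 vs 15. The documents do not support it as an expectation. Rises and falls are different PTs and would print on separate rows. SAP 7.5.1.9 neither says that both are in the group nor clearly plans a group total. Cancellation needs fewer falls on mirabegron, whereas Protocol 1.4.3 reports tamsulosin exposure about 60% higher and lower diastolic pressure with the combination, which would suggest more falls, if anything. That section also calls the diastolic effect small and free of orthostatic symptoms, in a study of mirabegron 100 mg/day and tamsulosin 0.4 mg/day. Likewise "The risks of QT prolongation, increased heart rate, or increased blood pressure are greater with increasing exposure" refers, in the words that follow it, to doses above the therapeutic range.

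A reader might also infer that a spread signal is never estimated. That goes too far, since its components are estimated under SAP 7.5.1.2.

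**Conclusion.** The point holds in a limited form. SAP 7.5.1.9 does not define its groups by term, gives blood pressure no direction, and plans no group-level difference between arms, while routine TEAE tables get one. SAP 7.5.1.2 does not necessarily fill the gap, because related terms can cross SOCs.

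The size depends entirely on assumed event rates. Over the rates tried, power for a group total is 53% to 89%, against 3% to 20% for a single term and 12% to 59% for at least one of four. These figures assume no man contributes to two terms, about 275 per arm, and an excess in the same direction on every term. Overlap between terms or a smaller safety set would reduce the advantage. Neither cancellation of opposite effects nor a complete absence of estimates is shown. The primary analysis is not affected.

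**What to change.** In SAP 7.5.1.9, before unblinding:
- List the MedDRA 18.1 terms, or a named query, for each special-interest group.
- Replace the blood-pressure group with two groups, increase and decrease, and state where orthostatic events and syncope are counted.
- For each group add one row that counts each subject once, by arm, with the mirabegron-minus-placebo risk difference and the exact unconditional 95% CI already used in SAP 7.5.1.1 and 7.5.1.2.
- Keep the SOC and PT rows beneath.

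The cost is about four summary rows from data already coded, plus the work of agreeing the term lists while still blinded. No new data are needed.
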